3.4.3. SUBGROUP ANALYSIS DEFINED BY GENDER

For gender subgroups (Male vs Female), estimates of significant hypotensive (vasovagal/hypovolemia) AE incidence rates along with their 95% CIs will be reported separately per experimental and control arms. Estimation will be conducted using Agresti-Coull method (Agresti, 1998). Sensitivity analysis will be conducted using exact method based on a binomial distribution, and Wald method with or without continuity correction. If data allow, additional model based analysis will be performed with the approach outlined in the primary analysis section with introduction of additional categorical covariate representing gender subgroups.

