3.1.1. STATISTICAL ANALYSIS METHOD

Given the nature of the data where donors contribute multiple data samples (donations), Generalized Estimation Equations Logistic Regression (GEE Logistic) framework for the repeat measures will be used (Halekoh, 2006; Yan J, 2004). The regression equation is presented below with Patient ID representing the random effect, and plasmapheresis method (study group) being fixed effect. Additional covariates are age, gender, BMI, and first-time donor status.

 $Logit(P(AE_{i,t}=1)) = \beta_0 + \beta_{Treatment} \times Treatment_i + \beta_{Age} \times Age_{i,t} + \beta_{Gender} \times Gender_i + \beta_{First \ Comer} \times First \ comer_{i,t} + \beta_{BMI} \times BMI_{i,t} + \varepsilon_{i,t},$

Corr(AE_{i,j}, AE_{i,k}) is exchangeable across all donors.

$$Corr(AE) = \begin{bmatrix} 1 & \gamma & \gamma & \gamma \\ \gamma & 1 & \gamma & \gamma \\ \gamma & \gamma & 1 & \gamma \\ \gamma & \gamma & \gamma & 1 \end{bmatrix}$$

Statistical Analysis Plan Version: 1.0 Date: 26-Apr-2020

AE represents the occurrence of a hypotensive AE (at least one), during the plasmapheresis procedure. *Treatment* is the variable representing plasmapheresis group (1=Experimental group, 0=Control group). For the *Gender* variable 1=Female, 0=Male. In *First comer* variable 1=First-time donor and 0=Repeat donor. First-time donors are those who have never undergone a plasmapheresis procedure. Age and BMI are continuous variables. i represents subject ID and t represents donation number for the given i subject.

Correlation structure within patients will be assumed to be exchangeable. Derivation of the final correlation model is currently in progress. The correlation structure can also be defined with the use of the historic data from the current study centers.

The above modeling will be used to obtain estimates of difference in proportions of significant hypotensive (vasovagal/hypovolemia) AE rates ($P_{Exper} - P_{Ctrl}$) in experimental and control groups along with its one-sided 97.5% upper limit of the CI calculated with Wald method.

[figure not shown]

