3.4.1. SUBGROUP ANALYSIS DEFINED BY THE FIRST-TIME DONOR STATUS

First-time donors are defined as those who have never undergone plasmapheresis prior to the study. This status will be collected as combination of the donation site historic records and self-reporting by study subjects. This information will be collected prior to randomization as follows: If the donor previously donated at the clinical site then he/she will be automatically in the repeat donor group. If no record of prior donation exists at the site, then donor will self-report the first-time donor status.

There will be two separate analyses for these subgroups performed as follows:

- *Analysis one*: Incidence rates of significant hypotensive (vasovagal/hypovolemia) AE will be compared between the experimental and control arms separately in the first-time and repeat donors, using the data from the first donations only.
- *Analysis two*: Incidence rates of significant hypotensive (vasovagal/hypovolemia) AE will be compared between the experimental and control arms separately in the first-time and repeat donors, using the data from entire ITT dataset (i.e. all donation).

ClinStatDevice

Statistical Analysis Plan Version: 1.0 Date: 26-Apr-2020

For analyses one and two estimates of significant hypotensive (vasovagal/hypovolemia) AE incidence rates along with their 95% CIs will be reported for all the subgroups. Estimation will be conducted using Agresti-Coull method (Agresti, 1998). Sensitivity analysis will be conducted using exact method based on a binomial distribution, and Wald method with or without continuity correction. If data allow, additional model based analysis will be performed with the approach outlined in the primary analysis section with introduction of additional categorical covariate representing the first-time donor status (first-time donor=0, repeat donor=1). The coefficient estimate associated with this covariate will be reported along with its 95% CI.

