3.4.2. SUBGROUP ANALYSIS DEFINED BY WEIGHT AND BMI

Information on Donors' weight will be collected prior to each donation. Three weight and three BMI groups will be defined.

- High weight group: Donors with weight more than 130lbs throughout the study;
- Low weight group: Donors with weight less or equal to 130lbs throughout the study;
- Borderline weight group: Donors who will have their weight group changed during the study (i.e. their weight will pass 130lbs threshold);
- High BMI group: Donors with BMI more than 30 throughout the study;
- Low BMI group: Donors with BMI less or equal to 30 throughout the study;
- Borderline BMI group: Donors who will have their BMI group changed during the study (i.e. their BMI will pass 30 threshold).

ClinStat Device

Statistical Analysis Plan Version: 1.0 Date: 26-Apr-2020

For low and high BMI and weight subgroups estimates of significant hypotensive (vasovagal/hypovolemia) AE incidence rates along with their 95% CIs will be reported separately per experimental and control arms. Estimation will be conducted using Agresti-Coull method (Agresti, 1998). Sensitivity analysis will be conducted using exact method based on a binomial distribution, and Wald method with or without continuity correction. If data allow, additional model based analysis will be performed with the approach outlined in the primary analysis section with introduction of additional categorical covariate representing weight (or BMI) subgroups. Data of the borderline groups will be analyzed separately as deemed appropriate.

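### SAP 3.4.2 classes donors by weight and BMI values recorded after randomisation, and the optional subgroup models in SAP 3.4.1 to 3.4.3 give no PPN-control contrast by subgroup

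*SAP*

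**What the plan says.** Protocol 4.2 and 5.2 ask for the rate of significant hypotensive events in two weight groups (cut at 130 lb) and two BMI groups (cut at 30). Protocol 9.5 makes subgroup analysis descriptive. SAP 3.4 lists the same two-way splits, but SAP 3.4.2 says "Three weight and three BMI groups will be defined". There a donor is low or high only if every recorded value stays on one side of the cut-off; a donor who crosses it is borderline. Rates by arm with 95% CIs are promised for low and high. The analysis of borderline donors is left open. Weight is measured before each donation.

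The main output for every subgroup variable is the rate in each arm with its 95% CI. For first-time status the SAP adds that the rates "will be compared between the experimental and control arms separately in the first-time and repeat donors". If the data allow, a model is also fitted, namely the primary model plus one term: "with introduction of additional categorical covariate representing the first-time donor status" in 3.4.1, a weight or BMI class in 3.4.2, and "with introduction of additional categorical covariate representing gender subgroups" in 3.4.3. In 3.4.1, "The coefficient estimate associated with this covariate will be reported along with its 95% CI".

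The primary model in SAP 3.1.1 already holds two of these variables: "Additional covariates are age, gender, BMI, and first-time donor status". It indexes first-time status by donor and donation ("i represents subject ID and t represents donation number for the given i subject") and codes first-time as 1. SAP 3.4.1 codes first-time as 0 and fixes status per donor: "First-time donors are defined as those who have never undergone plasmapheresis prior to the study".

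**The concern.** Subgroups in a randomised comparison are best fixed before any study procedure. Under SAP 3.4.2 a donor's class is known only at the end, and it depends on how often the donor came back: each further donation is another chance to cross 130 lb. The low-weight rate, a protocol secondary endpoint, is then reported in a narrower population selected on follow-up. Weight and BMI matter to readers here because PPN sets the target from body size. Protocol 2.1 expects lower targets for about 23.5% of donors, who on average weigh less than the donor population.

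The models raise a separate point. Without a treatment-by-subgroup term, a model estimates one common PPN odds ratio and cannot show whether the effect differs by subgroup. The coefficient promised in 3.4.1 compares first-time with repeat donors, not PPN with control.

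**Working it through.** **Inputs.** SAP Appendix 2: weight is truncated normal (211.2, SD 50.85, 110 to 400 lb); donations per donor are truncated Poisson(4), 1 to 24; 35.7% are female. SAP 5: 24,000 donations and a rate of 0.0015, so 12,000 donations and 18 events per arm. *Assumption, not in the documents:* each recorded weight is the donor's own mean plus independent normal noise with SD s = 2.5 lb, range 1 to 5.

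**Check on the inputs.** The plan gives no subgroup figure to reproduce. The truncated distributions have means of 214.0 lb and 4.07 donations. SAP Appendix 2, Table 4 shows 213.8 and 214.1 lb, and 4.06 and 4.04 donations.

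**1. Class size.** For a donor of mean weight w, the chance that one recorded weight is at or below 130 lb is q(w) = Φ((130 − w)/s). Let m(n) = E[q^n], the chance that n weights are all low.
- Share of donations, classed at first donation: m(1).
- Share of donations, classed over the whole study: Σ n·P(n)·m(n) / Σ n·P(n).
- Share of initially low donors who become borderline with n donations: 1 − m(n)/m(1).

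| s (lb) | Low at first donation, of 24,000 | Low throughout | Change | Expected events per arm |
|---|---|---|---|---|
| 1 | 784 | 726 | −7% | 0.59 → 0.54 |
| 2.5 | 788 | 645 | −18% | 0.59 → 0.48 |
| 5 | 804 | 523 | −35% | 0.60 → 0.39 |

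Events per arm are half the donations times 0.0015, for example 645/2 × 0.0015 = 0.48. At s = 2.5 lb, 10% of initially low donors with two donations become borderline and 17% of those with four. With one donation the share is zero whatever s is. For BMI, simulation with the Appendix 2 heights makes about 3.4% of donors borderline (1.4% to 6.8%).

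**2. Reported rate if donors stop after an event.** SAP Appendix 2 assumes this for its simulation; I read it as no further donations. A donor with an event at donation k then has only k weights and stays low with chance m(k) instead of m(n). With p = 0.0015, the class rate is expected events over expected donations:
- events: Σ P(n) Σ(k ≤ n) (1−p)^(k−1)·p·m(k)
- donations: Σ P(n) [ Σ(k ≤ n) (1−p)^(k−1)·p·k·m(k) + (1−p)^n·n·m(n) ]

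This gives 0.1545%, 0.1625% and 0.1797% at s = 1, 2.5 and 5 lb, against a true 0.150%. Classing at first donation returns 0.150%. If donors do not stop, and events are unrelated to the weight noise, both definitions return 0.150%.

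**3. Optional models.** The primary design has 6 columns (intercept, treatment, age, gender, first-time status, BMI) and rank 6.
- Add gender: 7 columns, rank 6. The model holds β·G + β′·G = (β + β′)·G, so only the sum is estimable and the PPN estimate does not change.
- Add reverse-coded first-time status, 1 − F: this equals the intercept column minus F, so the rank is 6 if F is the same variable. That is so if the donor-level definition in 3.4.1 is used in 3.1.1, and in analysis one, which uses first donations only.
- Add weight class or categorical BMI: rank 7, so estimable, but as a main effect only.
- Add treatment × gender: rank 7, so estimable.

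Illustration with the Appendix 2 sex rates (0.003831 female, 0.001145 male) and hypothetical PPN odds ratios of 2 in women and 0.5 in men: the planned model returns one odds ratio of 1.48, with or without the duplicate. The interaction model recovers 0.50 in men and a ratio of about 4.0.

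**4. Precision of an interaction.** Gender splits the 18 events per arm in proportion to 0.357 × 0.003831 = 0.00137 and 0.643 × 0.001145 = 0.00074, which is 11.7 and 6.3. The SE of the log ratio of odds ratios is √(2/11.7 + 2/6.3) = 0.70. For a ratio of 2 (log 0.693), two-sided 5% power is about 17%. For BMI (42.5% at or below 30; 7.65 and 10.35 events) the SE is 0.67 and power about 18%. For weight (0.59 and 17.4 events) the SE is 1.9 and power about 7%. These ignore within-donor correlation.

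**The case against.** The case on the other side is strong on consequence. Subgroup analysis is descriptive under protocol 9.5, the models are conditional on the data, and SAP 3.4 already warns of low power. A reader might infer that the missing interaction departs from the protocol or leaves the subgroup objectives unmet. The documents do not support that: the rates by arm within each subgroup meet the descriptive aim. The duplicate gender term leaves the PPN estimate as it was.

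On the classes, protocol 9 lets the SAP modify its plans, the protocol does not say which weight counts, and 3.4.2 keeps the cut-offs. Borderline donors are analysed separately, so it would be wrong to read the rule as discarding them. All of this stands. It does not reconcile SAP 3.4 with SAP 3.4.2, and the promised low and high rates do not cover every donation. SAP 3.2 defers detail on other secondary endpoints to later SAP versions, which is an opportunity to correct the text, but 3.4.2 is already specific. Classing each donation by its own weight is also natural, because the endpoint is per donation; that belongs in the plan as a sensitivity analysis.

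Two stronger readings are tempting. One is that the arms are compared with bias. The same rule applies to both arms, and the documents do not show that PPN alters recorded weight or return frequency. The other is that Appendix 2 shows how far the first-time coefficient moves between the two definitions of status. It does not: it never says whether the first-comer rates apply to the first donation only or to all of that donor's donations, and the answer depends on which is meant.

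**Conclusion.** The point holds as a matter of specification, at low severity. SAP 3.4.2 conflicts with SAP 3.4 and with the protocol's two groups, and it makes membership depend on post-randomisation weights and the number of donations. That dependence follows from the text. Its size (18% of low-weight donations lost, 7% to 35%) rests on the assumed visit-to-visit SD, and the expected rate of 0.155% to 0.180% against a true 0.150% also needs donors to stop after an event. With under one low-weight event expected per arm under either definition, neither effect would be visible in the data.

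The optional models in 3.4.1 to 3.4.3 supply no PPN-control contrast by subgroup. The gender term is an exact duplicate and cannot be estimated. The first-time term is a reverse-coded repeat, exact if status is defined per donor in both sections. The planned descriptive rates and the primary non-inferiority conclusion are unaffected.

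**What to change.** - **SAP 3.4.2:** classify weight and BMI at the first study donation into the protocol's two groups, add per-donation classification as a sensitivity analysis, and drop the borderline classes.
- **SAP 3.1.1 and 3.4.1:** use one definition and one coding of first-time status.
- **Gender, BMI and first-time status (analysis two only):** replace the added covariate with a treatment-by-subgroup term where events allow, and report the PPN-control difference in each subgroup with its CI, labelled exploratory. Otherwise delete the optional model and keep the planned rates by arm.
- **Weight:** report rates by arm only.

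The cost is SAP wording; the data are already to be collected. The drawback is that the interaction estimates will be very imprecise, with roughly 20% power for a ratio of odds ratios of 2, so they must not be read as evidence that the effect is the same across subgroups.

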3.5. SAFETY ANALYSIS

Statistical Analysis Plan Version: 1.0 Date: 26-Apr-2020

All AEs will be captured per established site procedures in compliance with IQPP standards and with Code of Federal Regulations (CFR). Safety analysis will be conducted on ITT population. Sensitivity analysis will be conducted on MITT population.

Investigators and sponsor physicians will be reviewing individual subject data throughout the conduct of the trial to ensure subjects' well-being.

Listings of all AEs will be presented. It will include information on occurrence and resolution of AEs: time/date, description and symptoms, study group, etc.

The frequency of AEs will be calculated and summarized. The results will be presented and visualized by IQPP categories and study groups using frequency plots and summary tables. If appropriate, individual AE profiles of subjects will be visualized as well. Comprehensive statistical summaries and comparisons will be presented by a study arm, adverse event types (e.g., hypotensive, citrate reactions, phlebotomy-related), and severity, as defined by plasma center adverse event reporting system, based on IQPP definitions. Further safety analysis will include an analysis of the collected plasma volumes at the donations associated with significant or severe AEs. The analysis will be based on estimating the distribution of collected plasma volumes by study arms. Statistical summaries (mean, median, range) will be presented for collected plasma volumes. In addition, the collected plasma volume will be compared with the target plasma volume calculated using control arm algorithm.

Safety events that trigger withdrawal of a subject will be presented by means of a listing, visual summaries, and appropriate statistical analysis.

Statistical Analysis Plan Version: 1.0 Date: 26-Apr-2020

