1.2.3. RANDOMIZATION

Donors will be randomized 1:1 to the experimental or control groups. As repeat donations by the same donor are expected, the donor will remain in the same study group during the entire course of the clinical trial.

The randomization will target equal allocation of the number of donors in each study group per site. Adverse Event (AE) incidence rates and the expected proportions in the sample groups are expected to be drastically different between the following groups: Males vs females and first-time

Statistical Analysis Plan Version: 1.0 Date: 26-Apr-2020

donors vs repeat donors. Thus, randomization will be further stratified by the donor's gender and first-time donor status. As the expected number of repeat donations is expected to be highly correlated with the AE incidence, stratification by expected number of repeat donations for the repeat donor groups might be done as well. This final step of the stratification will be possible under the condition of the availability of historic data through which calculation of expected number of donations for repeat donors could be completed.

Stratified permuted block randomization procedure with variable block sizes will be used. The sizes of the blocks will randomly vary with possible values of 6, 8 or 10.

Allocation of subjects to clinical trial groups will proceed based on the block randomization procedure as outlined above. Once subjects are enrolled, they will be randomly assigned to the experimental or control group and the assignment information will be synchronized with the NexLynk® system. The randomization system will provide a confirmation report containing the subject number and the randomization code. Sponsor will be monitoring the implementation of the randomization procedure for the QC purposes.

Allocation Miss-Assignment means administration of a study procedure other than that which was provided by the randomization assignment. Example: a subject was randomized to the Control group but received the Experimental procedure.

In the event of a protocol deviation caused by Allocation Miss-Assignment the following procedure will be used:

• If the Allocation Miss-Assignment happens at the first donation, the donor will be allowed to continue donating to the study group associated with the administered

ClinStatDevice

Statistical Analysis Plan Version: 1.0 Date: 26-Apr-2020

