procedure. Their study group assignment will be changed to the administered procedure group and the donor will be expected to donate only in this study group.

• If the donor happens to donate in both study groups (Allocation Miss-Assignment happens after the first donation or it happens twice) the donor will be discontinued. The study group associated with the donor will follow the procedure that the donor administered at the first donation.

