2.2. DEFINITIONS OF ANALYSIS DATA SETS

2.2.1. DEFINITIONS

Study Donor is defined as a study participant who consented to the study and was randomized to a study procedure (control or experimental).

Statistical Analysis Plan Version: 1.0 Date: 26-Apr-2020

Study Donation is defined as a donation that took place during the course of the study and is associated with the study donor.

Non-Study Donation is defined as a donation that took place either before the study start date or after the last date of the study.

Study Adverse Event is defined as an adverse event that was reported to be associated with the study donation.

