2.2.2. STUDY POPULATIONS

The ITT data set will consist of all study donations were the apheresis procedure was started by "Begin Draw" on the NexSys® PCS device. The ITT population will include all Study Adverse Events.

The Modified Intent to Treat (MITT) data set is a subset of the ITT data set which consists of all complete study donations, as well as all donations associated with a moderate or severe adverse event [not just hypotensive (vasovagal/hypovolemia)] defined according to the IQPP and associated with the study donations. A donation is considered complete if the total plasma volume collected is at least 200 mL. A donation is considered incomplete if the total plasma volume collected is less than 200 mL.

The Per-Protocol (PP) data set will consist of all donations without major protocol deviations where the apheresis procedure is successfully completed collecting at least 90% of the target plasma volume, as well as all study donations associated with a moderate or severe adverse event [not just hypotensive (vasovagal/hypovolemia)] defined according to the IQPP.

Statistical Analysis Plan Version: 1.0 Date: 26-Apr-2020

The Extended AE Population (EAEP) is defined as consisting of ITT population with the addition of all the AEs that were reported as associated with Non-Study donations in donors previously enrolled in the study and reported within two calendar weeks post study last day.

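### The SAP 3.5 safety tables follow the donor's study group, so an adverse event in a later wrong-procedure donation is shown under the procedure not given; the expected effect is small and the fix is cheap

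*SAP*

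**What the plan says.** SAP 3.5 sets the population for safety: "Safety analysis will be conducted on ITT population". MITT is its only sensitivity set. For adverse event frequencies it says "The results will be presented and visualized by IQPP categories and study groups using frequency plots and summary tables".

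SAP 1.2.3 defines the error in question: "Allocation Miss-Assignment means administration of a study procedure other than that which was provided by the randomization assignment". It then gives two rules.

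- Error at the first donation: "Their study group assignment will be changed to the administered procedure group". The donor continues in that group.
- Donor ends up with both procedures: the donor is discontinued, and "The study group associated with the donor will follow the procedure that the donor administered at the first donation".

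SAP 2.2.1 sets no condition on the procedure run: "Study Donation is defined as a donation that took place during the course of the study and is associated with the study donor". Under SAP 2.2.2 the ITT set takes every such donation that reached Begin Draw, and "The ITT population will include all Study Adverse Events".

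**The concern.** The trial asks whether a collection procedure is safe, and the safety tables are where a reader looks to see what happened under each procedure. Suppose a control donor is given a PPN collection at the third donation and has a reaction. The rules above keep that donation in ITT, and the donor's group remains Control. The reaction is then counted under Control. The reverse case works the same way.

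The two rules in SAP 1.2.3 also treat similar errors differently. A first-donation error moves the donor to the procedure received, so group and procedure agree. A later error does not. The resulting grouping is neither as randomized nor as received donation by donation. This point concerns only the later errors, where the group shown and the procedure given differ.

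**Working it through.** **Step 1: does any analysis set put the donation under the procedure received?**

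| Place | Treatment of a later wrong-procedure donation |
|---|---|
| ITT (SAP 2.2.2) | Kept, with all its adverse events; no regrouping |
| MITT (SAP 2.2.2) | Subset of ITT; no regrouping |
| Per-protocol (SAP 2.2.2) | Drops major deviations but adds back donations with a moderate or severe adverse event; not used in SAP 3.5 |
| Extended AE population (SAP 2.2.2) | ITT plus events from non-study donations; no regrouping |
| Primary model (SAP 3.1.1) | Treatment carries the donor index only; age and BMI carry donor and donation |
| AE listing (SAP 3.5) | Names study group; procedure received is not named |
| Assigned versus actual (SAP 3.3) | Exploratory risk indicator only |
| Protocol 9.9 | Summaries by study arm; does not settle the point |

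None regroups the donation.

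**Step 2: inputs for the size.** From SAP 5: 24,000 donations, 6,000 donors, a significant-event rate of 0.0015 per donation and a margin of 0.0015. From SAP 3.2: a severe-event rate of 1/10,000. Equal arms give 12,000 donations each. The mis-assignment rate is not in the documents and is assumed below.

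**Step 3: the plan's own figures.**

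- Expected severe events per arm: 12,000 / 10,000 = 1.2, as SAP 3.2 states.
- Power at zero difference: SE = √(2 × 0.0015 × 0.9985 / 12,000) = 0.0005. Then Φ(0.0015/SE − 1.96) = 85.1%, against the stated figure of more than 85%.

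**Step 4: expected misplaced events.** With one crossed donation per affected donor, expected misplaced events = crossed donations × rate. The 0.0030 column is the assumed rate plus the margin.

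| Donors affected (assumed) | Crossed donations | Significant, at 0.0015 | Significant, at 0.0030 | Severe, at 1/10,000 | Chance of ≥1 significant, at 0.0015 |
|---|---|---|---|---|---|
| 0.1% | 6 | 0.009 | 0.018 | 0.0006 | 0.9% |
| 1% | 60 | 0.09 | 0.18 | 0.006 | 8.6% |
| 2% (0.5% of donations) | 120 | 0.18 | 0.36 | 0.012 | 16.5% |
| 5% | 300 | 0.45 | 0.90 | 0.030 | 36% |

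For comparison, 12,000 × 0.0015 = 18 significant events are expected per arm.

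**Step 5: direction.** If a share q of donations is crossed equally in both directions, a true difference d appears as d × (1 − 2q). With d = 0.0015 and q = 0.005, that is 0.0015 × 0.99 = 0.001485. With d = 0 there is no shift on average. A single misplaced event moves the difference towards whichever arm it is booked under.

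**The case against.** **The text is not fully explicit.** SAP 1.2.3 fixes the group of the donor, but it also speaks of donating in both study groups, which uses the term at donation level. SAP 3.5 does not say which use governs its tables. This stands as a caveat: the misattribution is the natural reading, not a quoted rule. It does not remove the need for a rule.

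**Errors are controlled and visible.** Protocol 8.3 provides arm-specific product codes, a check by the phlebotomist and separate device locations. Protocol 8.2 makes group assignment a proficiency criterion. Protocol 9.8 and SAP 3.3 track assigned against actual, and Protocol 11.1 requires every deviation to be reported. SAP 3.5 also compares collected volume with the control-algorithm target at donations with significant or severe events, which may expose a PPN collection shown under Control. All of this should keep the number low, but none of it moves an event to the right column.

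**Stronger readings that a reader might infer.**

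- *One misplaced event could decide the trial.* Moving one event changes the rate difference by 1/12,000 + 1/12,000 = 0.000167, or 11% of the margin. But the margin belongs to the primary test in SAP 3.1.2. SAP 3.5 has no margin and no pass/fail rule, and the primary analysis properly stays on ITT.
- *One misplaced severe event could reverse the arms.* This is possible with 1.2 expected per arm. At 120 crossed donations, however, only 0.012 severe events would be misplaced, about a 1% chance of even one.
- *The rule favours a finding of no worse.* This is true only on average, and only if PPN carries the higher rate.
- *Stopping decisions are distorted.* They are not. Protocol 9.10 and SAP 3.6 count deaths and severe events over both arms and lead to unblinded DMC review.

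**Conclusion.** The point holds in limited form. On the natural reading of SAP 1.2.3, 2.2 and 3.5, an adverse event in a later wrong-procedure donation is reported under the procedure not received, and no defined set corrects this. The documents do not show a material bias. Discontinuing the donor normally limits the exposure to one donation each, and 120 such donations would misplace about 0.2 to 0.4 significant events. That figure rests on an assumed crossing rate, on the plan's rate of 0.0015 (or 0.0030 at the margin), and on one crossed donation per affected donor. Minor, citrate and phlebotomy events are tabulated in SAP 3.5 too, but the plan gives no rates from which to size them. The case for change is that safety tables should show what happened under each procedure, and that attribution of an individual event should be settled before the data are seen.

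**What to change.** - In SAP 2.2.2, define a safety set of all study donations with Begin Draw, grouped by the procedure actually administered at that donation.
- Use it for the SAP 3.5 adverse event tables.
- Add procedure received to the adverse event listing, and list every wrong-procedure donation with its adverse events.
- Keep ITT for the primary analysis. A run of the primary comparison by procedure received is optional and supportive only.

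The cost is SAP wording and one grouping variable. The procedure administered must already be known to apply SAP 1.2.3, and the error is reportable as a deviation under Protocol 11.1. The downside is that safety and primary tables may differ by a few donations, which a footnote can explain.
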